# 4.3. Randomization and study procedures

If patients fulfill all inclusion criteria, with no exclusion criteria and provide informed consent, they will be randomized in a 1:1 fashion into the intervention group or the control group according to a pre-specified, computer-generated, web-based randomization scheme using the secuTrial© Software (managed and secured by the Clinical trial Unit of the University of Basel). The randomization will be stratified for the site and initial NRS (Appendix 2). In both study groups, all patients will be re-assessed daily by the nutritional specialist to re-evaluate nutritional intake and whether nutritional targets are met. If patients in the intervention group do not reach the nutritional targets (<75%), their nutritional strategy will be escalated according to the nutritional guidelines.

We will systematically collect blood samples at admission (day 0) and on inpatient days 2, 4, 6 and 8 for later batch measurement of nutritional markers and other biomarkers. If clinically indicated, there will be pre-prandial measurement of blood glucose levels 4 times daily and insulin treatment in all patients as part of usual clinical practice. There will also be regular measurement of nutritional factors in blood and possibly 24 hour urine to assess the effectiveness of nutritional therapy (see CRF for further details).

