#### 1.7. Patient information and informed consent

The investigators or other authorised individuals personal will explain to each participant the nature of the study, its purpose, the procedures involved, the expected duration, the potential risks and benefits and any discomfort it may entail. Each participant will be informed that the participation in the study is voluntary and that he/she may withdraw from the study at any time and that withdrawal of consent will not affect his/her subsequent medical assistance and treatment.

The participant must be informed that his/her medical records may be examined by authorised individuals other than their treating physician. All participants for the study will be provided a participant information sheet and a consent form describing the study and providing sufficient information for participant to make an informed decision about their participation in the study. The patient information sheet and the consent form will be submitted to the ethical review board to be reviewed and approved. The formal consent of a participant, using the approved consent form, must be obtained before the participant is submitted to any study procedure.

The participant should read and consider the statement before signing and dating the informed consent form, and should be given a copy of the signed document. The consent form must also be signed and dated by the investigator (or his designee) and it will be retained as part of the study records.

The investigator affirms and upholds the principle of the participant's right to privacy and that they shall comply with applicable privacy laws. Especially, anonymity of the participants shall be guaranteed when presenting the data at scientific meetings or publishing them in scientific journals.

Individual subject medical information obtained as a result of this study is considered confidential and disclosure to third parties is prohibited. Subject confidentiality will be further ensured by utilising subject identification code numbers to correspond to treatment data in the computer files.

For data verification purposes, authorised representatives of the Sponsor (-Investigator), a competent authority or an ethics committee may require direct access to parts of the medical records relevant to the study, including participants' medical history.

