#### Secondary endpoints will be defined as follows:

- (a) each single component of the primary endpoint at day 30
- (b) each single component of the primary endpoint and the combined endpoint at short term, ie, at day 10 or hospital discharge whatever comes first
- (c) each single component of the primary endpoint and the combined endpoint at long term term, ie, at day 180
- (d) short-term nutritional and functional outcomes from inclusion to day 10 or hospital discharge (whatever comes first) including nutritional intake, improvement in muscle strength measured with handgrip strength, lean body mass, changes in undernutrition markers (pre-albumin, retinol-binding protein, body weight, BMI)];

- (e) hospital outcomes measured at hospital discharge defined as total hospital LOS, discharge home vs. post-acute care facility, new decubital ulcer;
- (f) Improvement in quality of life measured on admission and at 30-day and 180-day using the EuroQol Group 5-Dimension Self-Report Questionnaire (Appendix 3) and selected items from the Functional Assessment Anorexia-Cancer Therapy [FAACT] questionnaire),

Safety endpoints including side effects from nutritional therapy will be assessed daily until hospital discharge. A causal relationship with the trial will be rated by two study team members as unrelated / unlikely / possible / probable / definitely / not assessable. The following side effects were defined:

- a) Adverse gastrointestinal effects (diarrhea, nausea, vomiting, abdominal pain)
- b) Complications due to tube feeding or center catheter for parenteral nutrition,
- c) Refeeding syndrome,
- d) Liver or gall bladder dysfunction
- e) Hyperglycemia (defined as glucose levels >12mmol/l or persistent levels >10mmol/l in patients without diabetes or well controlled diabetes)

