# 5. Selection of trial subjects

# 5.1. Recruitment

Upon hospital admission, consecutive adult (age ≥18 years) medical inpatients will be screened for undernutrition risk by the house nursing and /or physician staff, using the well-validated NRS, 2002 edition, as shown in Appendix 2.

Based on this routine screening instrument, we will check daily for eligible patients using the hospital medical information system. Patients can be included in this trial within 24-48 hours of admission if they fulfill the following inclusion criteria

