# 7. Assessment of Safety

# 7.1. Risks of the study

We consider the risks of this study to be minimal, for the following reasons:

- Blood Loss: 7.5ml of EDTA-plasma and 7.5ml of serum as well as one additional tube (7.5ml) for determination of genetic markers will be additionally drawn on admission. All other blood draws are part of clinical routine
- Whether or not nutritional therapy has a benefit in acutely ill medical inpatients remains unclear.
   Different smaller trials have not been able to demonstrate large improvements in patient outcomes in regard to mortality and/or morbidity.
- Risks of nutritional therapy include refeeding syndrome and risk associated with enteral and
  parenteral nutrition. We will do a careful monitoring for refeeding including daily clinical visits
  and routine blood work for electrolyte dysbalance. In case of refeeding syndrome, we will lower
  the amount of nutritional therapy (50%) and also treat with B-complex vitamins. We expect that
  only a minority of patients will receive enteral and parenteral nutrition (around 10%) and in these
  patients benefits may outweigh risks.

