#### 11. Ethical considerations

The study will be approved by the ethics committees of the participating hospitals.

This study will be conducted in compliance with the protocol approved by the IEC, and according to ICH-Good Clinical Practice standards. No deviation from the protocol will be implemented without prior review and approval of the IEC except where it may be necessary to eliminate an immediate hazard to a research subject. In such case, the deviation will be reported to the IEC as soon as possible. All enrolled patients will be asked to give written informed consent. In patients, in which "informed consent" is not feasible due to dementia or their acute medical condition, patients' next to kin can sign an assent form to state the presumptive will of the patient. In case, next of kin are not readily available, a treating physician – who must not be involved in the study – have to certify that there are no objections for inclusion in the study from his point of view. Only after these informed consent procedures the patient can be included in the study.

Importantly, despite strong associations between malnutrition and adverse clinical outcome, we believe that is ethically acceptable that the control group receive usual care treatment because there is uncertainty about the effectiveness and safety of nutritional therapy in this patient population. This important subject has been discussed among national experts in the field (i.e., collaborators) who all agree to this practice. This is also in accordance with a recent Swiss consensus ethical statement pointing out that "intake of standard food and fluids is a basic right of any patients", yet any sort of nutritional therapy must be viewed as a therapeutic measure and must therefore fulfill all criteria for such including proof of clinical effectiveness, safety and cost-effectiveness). For our patient population, such proofs is still missing and the main aim of this trial.

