**Statistical approach:** Detailed methodology for the statistical analyses will be documented in a statistical analysis plan. To investigate whether differential treatment effects exist in patient subgroups as defined above, we will include interaction terms into the statistical model and check for effect modification (see details in RCT section, statistical approach). For subgroups defined by biomarker levels, we will divide those levels into quartiles to check for robustness of results. All analyses will be predefined based on biological plausibility to avoid multiple testing. We will further define a derivation sample and a validation sample (1:1) for these analyses for reproducibility of results and decreased risk of chance findings. We will use a linear mixed model approach to assess the effect of nutrition on serial biomarker levels over the course of hospitalization.

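### Biomarker sampling is counted from hospital admission, but consent and treatment may start up to 48 hours later, so for patients included late the day-0 study draw cannot be taken as stated and day 2 can be a pre-treatment value

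*Protocol*

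**What the plan says.** Section 4.3 schedules the blood draws by hospital day: "We will systematically collect blood samples at admission (day 0) and on inpatient days 2, 4, 6 and 8 for later batch measurement". Four other parts of the protocol bear on that clock.

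- **Inclusion (5.1):** "Patients can be included in this trial within 24-48 hours of admission if they fulfill the following inclusion criteria". Appendix 4 gives the same 24-48 hour span for the nutritional risk screening itself.
- **Consent (1.7 and 11):** "The formal consent of a participant, using the approved consent form, must be obtained before the participant is submitted to any study procedure", and "Only after these informed consent procedures the patient can be included in the study".
- **Nature of the draws (7.1):** plasma, serum and genetic tubes "will be additionally drawn on admission. All other blood draws are part of clinical routine". The admission tubes are thus extra study blood, not leftover routine samples.
- **Analyses:** secondary endpoint (d) in section 4.2, which contains pre-albumin and retinol-binding protein, covers "short-term nutritional and functional outcomes from inclusion to day 10 or hospital discharge". Section 13.1 plans subgroups by admission markers and states: "We will use a linear mixed model approach to assess the effect of nutrition on serial biomarker levels over the course of hospitalization".

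The sampling days also differ between sections: 0, 2, 4, 6, 8 in 4.3; 0, 1, 3, 5, 7 in 13.1; admission and 3, 5, 7 in 13.3. Genetic tubes are drawn at admission according to 7.1 but at enrolment according to 13.4.

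**The concern.** The sampling schedule starts at hospital entry. The marker endpoint starts at inclusion, and treatment cannot start before inclusion. When the two origins are a day or two apart, two things follow. The first study tube, as scheduled, would have to be drawn before consent. And patients sampled on the same nominal day will have been treated for different lengths of time, some not at all on day 2.

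At stake are the change in pre-albumin and retinol-binding protein, the serial biomarker model and the subgroups by admission markers. All need a first sample that clearly precedes treatment, and the first two also need a time axis that reflects time on treatment. An analysis plan can re-index time if draw times are known, but it cannot supply a sample that was not taken at a useful moment.

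**Working it through.** The plan gives no figure for this, so there is nothing to reproduce. The check is timeline arithmetic.

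**Inputs.** Sampling days from section 4.3. Delay from admission to inclusion between 0 and 48 hours (5.1, read as an upper limit). Assumption: treatment starts at inclusion. Section 4.4 places the nutritional assessment after inclusion, so true exposure can only be shorter.

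**Step 1. Hours since inclusion at nominal day d** = 24 × d − delay.

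| Delay | Day 0 | Day 2 | Day 4 | Day 6 | Day 8 |
|---|---|---|---|---|---|
| 0 h | 0 | 48 | 96 | 144 | 192 |
| 24 h | −24 | 24 | 72 | 120 | 168 |
| 48 h | −48 | 0 | 48 | 96 | 144 |

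A negative entry is a study draw before consent, which section 1.7 rules out. At a 48-hour delay, day 2 is the moment of inclusion. If blood is drawn on a morning round (assumed 07:00) and the patient was admitted at 08:00, 14:00 or 22:00 with a 48-hour delay, the day-2 sample falls 1, 7 or 15 hours before inclusion.

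**Step 2. Mean exposure as a share of nominal time** = (24 × d − mean delay) / (24 × d). The protocol gives no delay distribution, so a range of assumptions is shown.

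| Assumed delay | Day 2 | Day 4 | Day 6 | Day 8 |
|---|---|---|---|---|
| Uniform 0-48 h (mean 24) | 24/48 = 50% | 72/96 = 75% | 120/144 = 83% | 168/192 = 88% |
| Uniform 24-48 h (mean 36) | 12/48 = 25% | 60/96 = 63% | 108/144 = 75% | 156/192 = 81% |
| All at 48 h | 0% | 48/96 = 50% | 96/144 = 67% | 144/192 = 75% |

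If an effect grows in proportion to exposure, these shares are also the fraction of the nominal-time effect that remains.

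**Step 3. The schedule in section 13.1**, to which the mixed model belongs. Hours since inclusion at days 1, 3, 5 and 7 are 24, 72, 120, 168 with no delay; 0, 48, 96, 144 with a 24-hour delay; and −24, 24, 72, 120 with a 48-hour delay. The pattern is the same, with the problem now sharpest at day 1.

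**Step 4. A cruder measure.** If a share f of patients has the day-2 sample before treatment, and the effect is equal in the rest, the day-2 arm difference is multiplied by about 1 − f: 0.9 at f = 0.1 and 0.7 at f = 0.3. Both values of f are assumptions.

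**The case against.** The strongest reply is that the protocol uses admission loosely to mean trial baseline. Genetic sampling is placed at admission in 7.1 and at enrolment in 13.4. Barthel decline runs from admission in 4.2, yet the baseline Barthel index is taken after inclusion in 4.4. If day 0 means enrolment, the conflict with consent disappears and the marker endpoint has the same origin. That reading is possible but not stated, and the later draws in 4.3 are still numbered by inpatient day. Sites could reasonably apply different clocks.

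Three stronger conclusions are tempting, and the documents support none of them.

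- *That the day-0 sample can never be taken on time.* Section 5.1 sets an upper limit; a patient who consents on the day of admission can be sampled that day.
- *That baseline blood will be drawn after treatment has begun.* No section says so. The protocol only leaves the order of first tube and first nutritional measure unstated, and the case report form, to which 4.3 refers, is not available here.
- *That the marker results are biased towards one arm.* The delay arises before randomisation and should be balanced. The arm contrast at a given inpatient day remains a valid comparison, though a weaker and less sharply defined one.

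It is also fair to say that draw-time fields and the time variable in the mixed model commonly belong in the case report form or the analysis plan. When the blood is drawn does not: the protocol fixes that.

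**Conclusion.** The concern holds for patients who are not consented on the day of admission. For them the day-0 study draw conflicts with the consent rule as written, and nominal day 2 lies 0 to 48 hours after inclusion for delays of 48 down to 0 hours, so it can be a pre-treatment value. How many patients this affects cannot be computed from the protocol.

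The loss is greatest at the first follow-up draw and shrinks later: half to three quarters of nominal exposure time at day 2, and 12.5 to 19% at day 8, under the two uniform assumptions. These figures rest on the assumed delay distribution and on treatment starting at inclusion; reading them as a loss of effect further assumes that the effect is proportional to exposure.

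The consequence is reduced precision and a blurred time axis for the nutritional-marker endpoint and the ancillary biomarker analyses. The primary endpoint and the sample size are untouched. The change is worth making because it is cheap and cannot be made after the blood has been drawn.

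**What to change.** - In section 4.3, define day 0 as the day of randomisation. Have the baseline tubes drawn after consent and before the first study nutritional measure, and count all later draws from randomisation in both arms.
- Record the actual time of each draw, so that time since randomisation can be used in the serial model.
- Choose one set of sampling days and carry it through sections 4.3, 13.1 and 13.3.
- Align the timing of the extra and genetic tubes in 7.1 with that in 13.4.
- If true admission values are wanted for the subgroups in 13.1, take them from routine admission laboratory results, where available, and label them as such.

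The cost is wording in these sections and, if not already present, a draw-time field in the case report form. The number of draws need not rise. The small downside is that draws counted from randomisation may coincide less often with routine ward blood sampling, on which 7.1 relies for everything after admission.

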# 13. Ancillary projects

# 13.1. Physio-pathological mechanisms of action of nutritional therapy

**Purpose:** To understand the physio-pathological mechanisms of action explaining how nutritional therapy exerts its effects on disease recovery in specific patient populations and illnesses. The large sample size and the diversity in medical diagnosis and comorbidities will offer the unique opportunity to study distinct effects of nutritional therapy.

**General approach:** Using patient data generated in the RCT, we will first look at how effects of nutritional therapy vary depending on age (quartiles), gender, medical illnesses (systemic infection, heart failure, renal failure, gastro-intestinal disease, tumor), BMI (<20, 20-25, >25-30, >30) and acuity (acute vs. chronic disease courses). We will also look at subgroups defined by admission nutritional / endocrine markers (e.g. initial pre-albumin, stress markers, inflammation blood biomarkers). In a second step, we will focus on specific patient populations to assess whether nutritional therapy has an effect on disease course. Specifically, we will focus on patients with systemic infections to study effects of nutritional therapy on the inflammatory response. We will look at biomarkers measured in blood samples collected from patients on admission and during follow up (inpatient days 0, 1, 3, 5 and 7). We will look at levels of inflammatory/infection biomarkers such as C-reactive protein (CRP) and PCT and stress markers such as cortisol and copeptin levels as surrogates for disease severity, recovery and medical outcome, respectively.

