To close this gap, we will study the influence of nutritional therapy on glucose homeostasis and insulin management as a possible explanation for the higher rates of complication and infection of patients with high caloric intake. Specifically, we will routinely collect information about glucose control, i.e., 4-timesdaily glucose measurements and insulin dose if applicable in all included patients. We hypothesize that hyperglycemia on admission and during inpatient treatment is associated with an adverse disease course, as evidenced by more pronounced inflammatory and stress responses and worse clinical outcomes. To test this hypothesis, we will first investigate the association of initial blood glucose concentrations with clinical outcomes including LOS, disease-specific complications, and mortality. Based on the initial glucose concentration, patients will be priori classified as having normal levels (reference group, blood glucose <7mmol/L), moderate hyperglycemia (blood glucose 7-11mmol/L) or severe hyperglycemia (blood glucose >11mmol/L) based on the classification in a recent publication. In patients with systemic infection, we will used blood levels of CRP and PCT and the white blood cells count at admission and on days 3, 5 and 7 to reflect the inflammatory response. In a second step, we will compare glucose metabolism between randomization arms and investigate whether glucose control with insulin may reduce any harmful effects exerted by hyperglycemia.

This ancillary project will shed light on the important interplay of nutritional therapy and glucose metabolism, and may help to generate preliminary data on the optimal use of insulin in this situation.

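### Blood-sampling days in sections 4.3, 13.1 and 13.3 agree only on day 0, and glucose measurement is conditional in 4.3 but universal in 13.3; one schedule, the same in both arms, should be stated

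*Protocol*

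**What the plan says.** **Blood sampling**
- Section 4.3 (study procedures): "We will systematically collect blood samples at admission (day 0) and on inpatient days 2, 4, 6 and 8". The samples are for later batch measurement of nutritional and other biomarkers.
- Section 13.1 (mechanisms): biomarkers come from samples taken "on admission and during follow up (inpatient days 0, 1, 3, 5 and 7". The planned analysis is: "We will use a linear mixed model approach to assess the effect of nutrition on serial biomarker levels over the course of hospitalization".
- Section 13.3 (glucose project): in patients with systemic infection, CRP, PCT and white cell count are used "at admission and on days 3, 5 and 7 to reflect the inflammatory response".
- Section 7.1 (risks): after listing the additional tubes taken on admission, it adds: "All other blood draws are part of clinical routine".

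**Glucose**
- Section 4.3: "If clinically indicated, there will be pre-prandial measurement of blood glucose levels 4 times daily and insulin treatment in all patients", which it describes as usual practice.
- Section 13.3: the project will collect "4-timesdaily glucose measurements and insulin dose if applicable in all included patients", and it goes on to plan a comparison of glucose metabolism between the randomised arms.

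**What depends on these data**
- Section 4.2 lists changes in pre-albumin and retinol-binding protein under secondary endpoint (d). It lists hyperglycaemia as side effect (e), defined as glucose above 12 mmol/l, or persistently above 10 mmol/l, in patients without diabetes or with well controlled diabetes.
- Section 6.2 states that patients and caregivers are unblinded. Blinded assessment applies at days 30 and 180, whereas side effects are assessed daily in hospital.

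**The concern.** A site cannot follow the day lists of 4.3 and 13.1 together. A follow-up sample not drawn on the intended day cannot be recovered later. If routine care decides which later samples exist, their availability may follow clinical need.

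The glucose wording matters because hyperglycaemia is defined by a threshold, so the chance of recording it rises with the number of measurements. Under the conditional reading, the people who decide on testing know the treatment arm. The protocol gives them reasons to test the intervention arm more: section 13.3 says that feeding may raise glucose further, and section 15 plans continuing education of caregivers about the potential risks of nutritional therapy. At stake are the hyperglycaemia safety comparison, the between-arm glucose comparison in 13.3, the serial-biomarker analysis in 13.1, and any section 4.2(d) markers measured in the same samples.

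**Working it through.** The protocol gives no figure of its own on this point, so the check sets the passages side by side and then works a labelled illustration.

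**1. Day lists**
- Section 4.3: {0, 2, 4, 6, 8}. Section 13.1: {0, 1, 3, 5, 7}. Section 13.3: {0, 3, 5, 7}, taking admission as day 0.
- 4.3 ∩ 13.1 = {0}. One of five analysis days has a scheduled sample; days 1, 3, 5 and 7 have none.
- 4.3 ∩ 13.3 = {0}. One of four matches.

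**2. Could it be only a numbering difference?** Subtracting 1 from {2, 4, 6, 8} gives {1, 3, 5, 7}, so the follow-up series are the same apart from one day. But both 4.3 and 13.1 name a day 0, and 4.3 ties it to admission. Shifting the whole 4.3 list back by one would put admission at day −1. The text therefore does not resolve the difference.

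**3. Does one day matter?** Section 5.1 allows inclusion within 24–48 hours of admission, and section 1.7 requires consent before any study procedure. Counting from admission, inclusion can fall as late as day 1 to day 2. A day 1 sample may therefore precede randomisation in some patients, which is why the definition of day 0 has to be fixed together with the days.

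**4. Study draws or routine draws?** Sections 7.1 and 4.3 are compatible if study material is taken at routine draws. In that case the sampling is systematic only as far as routine blood is taken on those days. If the later draws are made for the study, 7.1 omits them. The protocol does not say which applies.

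**5. Glucose ascertainment (illustration; every input is an assumption).** Let h be the true proportion with hyperglycaemia, equal in both arms, and m the share of those patients whose glucose is measured often enough to detect it. The recorded rate is h × m, so the recorded risk ratio is (h × m_I) / (h × m_C) = m_I / m_C.

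| m_I | m_C | Recorded rates, h = 10% | Recorded rates, h = 30% | Ratio |
|---|---|---|---|---|
| 80% | 80% | 8% vs 8% | 24% vs 24% | 1.00 |
| 80% | 60% | 8% vs 6% | 24% vs 18% | 1.33 |
| 80% | 50% | 8% vs 5% | 24% vs 15% | 1.60 |

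Equal monitoring under-counts cases but leaves the ratio at 1.00. The protocol states neither h nor either m, so no row of the table can be preferred.

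**The case against.** The strongest reply is that this is loose drafting, mostly in ancillary sections. The follow-up days are one day apart throughout, section 4.3 refers to the CRF for further detail on blood measurements, and a pilot is planned in which trial materials are validated (section 8.4). Much of that is fair, and it rules out several stronger readings that a reader might infer.

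- *Biomarker data will be missing.* Not supported. The mixed model as described names no days and can use whatever days are sampled. CRP and white cell count may come from routine blood work. Follow-up samples exist under either list; they may just not exist on the days named.
- *Section 7.1 contradicts 4.3.* Not established. Taking study material at routine draws satisfies both. What remains is that the source of the later samples is unstated.
- *Glucose is measured selectively but analysed in everyone.* Too strong. The sentence in 4.3 is conditional at the start and also refers to all patients, and 13.3 speaks of collecting values, not only of analysing them. If 13.3 governs, both arms are measured alike and the bias argument falls away.
- *Hyperglycaemia will appear falsely increased by some particular ratio.* Not derivable. The illustration depends entirely on its assumed monitoring shares. Testing on indication also tends to reach patients at higher risk, so fewer true cases would be missed than if testing were unrelated to risk.

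What stands against the reply is that the lists do conflict, renumbering does not reconcile them, and the conditional reading of 4.3 is open to an unblinded team.

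**Conclusion.** The point holds as an internal inconsistency with a possible bias attached. The three day lists share only day 0 (one of five time points in 13.1, one of four in 13.3), the source of later draws is unclear, and the glucose rule reads differently in 4.3 and 13.3. If 4.3 governs, serial values may be absent on the days the ancillary analyses name, and unequal glucose testing is plausible in an open feeding trial.

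A bias in the hyperglycaemia comparison requires two things: that testing follows indication, and that its frequency differs by arm. Neither is certain, the size cannot be obtained from the protocol, and the ratio is undistorted if monitoring is equal. The reach is limited to one safety endpoint, any secondary nutritional markers measured in these samples, and two ancillary projects. The primary endpoint and the sample size of 1,359 per group are untouched. It is worth correcting before the pilot because undrawn samples cannot be replaced.

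**What to change.** 1. Reconcile sections 4.3, 7.1, 13.1 and 13.3 into one list of sampling days, with one definition of day 0 (admission or inclusion) and a statement of whether each draw is a study draw or routine.
2. State once which patients have glucose recorded and when, and apply it identically in both arms. Which clinical rule that should be is for the investigators; this review does not choose it.
3. Report the number of glucose measurements per patient-day by arm next to the hyperglycaemia comparison.
4. Add a sensitivity comparison of hyperglycaemia restricted to values from time points scheduled identically in both arms, where such values exist. It should remain a sensitivity analysis. Nothing in the protocol shows that glucose can be read from the batch-stored samples, and about five isolated values could not establish persistent elevation.

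The cost is alignment of four sections and the matching CRF pages, plus one extra descriptive table and one sensitivity analysis. Nothing changes for the primary analysis.
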